3.2 END OF STUDY

The end of the study is defined as the date when the last patient, last visit (LPLV) occurs, that is when the last patient reaches the end-of-study visit (approximately 4 months after the last patient is enrolled). The end-of-study visit will occur 4 weeks after patient's last dose of study treatment, or earlier, if one of the following is documented for all treated patients: withdrawal from the study, loss to follow up or death.

3.3 RATIONALE FOR STUDY DESIGN

3.3.1 Rationale for Test Product Dosage

The study treatment dosing is consistent with the approved label of Recormon® and standard treatment guidelines.

As improvements in haemoglobin are usually noted 6–8 weeks after initiation of an adequate dose of ESA, a minimum 8-week treatment period was considered to be indicated.

3.3.2 Rationale for Patient Population

Several studies have proven the efficacy of the ESAs in eliciting erythroid response in low/int-1 MDS patients. The subset of MDS patients benefiting from ESA therapy is now well defined as the low-/int-1-risk group with sEPO of less than 500 mU/ml and a PRBC transfusion need of less than 4 units within 8 weeks prior to screening.

3.4 OUTCOME MEASURES

3.4.1 Efficacy Outcome Measures

The efficacy outcome measures for this study are as follows:

Primary Efficacy Outcomes:

- The cumulative proportion of patients achieving erythroid response at week 12 according to IWG 2006 definition as
 - Hb increase by ≥ 1.5 g/dL
 - Reduction of units of RBC transfusions by an absolute number of at least 4 RBC transfusions/8 weeks compared with the pre-treatment transfusion number in the previous 8 weeks. Only RBC transfusions given for a Hb of ≤ 9.0 g/dL pre-treatment will count in the RBC transfusion response evaluation

Secondary Efficacy Outcomes:

- % patients with platelet response (pre-treatment $< 100 \times 10^9/L$) at week 12 defined by IWG 2006 as following:
 - Absolute increase of $\geq 30 \times 10^9/L$ for patients starting with $> 20 \times 10^9/L$ platelets (Increase from $< 20 \times 10^9/L$ to $> 20 \times 10^9/L$ and by at least 100%)
- % patients with neutrophil response (pre-treatment $< 1.0 \times 10^9/L$) at week 12 defined by IWG 2006 as following;
 - At least 100% increase and an absolute increase $> 0.5 \times 10^9/L$

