Transfusion dependency affects quality of life and predicts shortened survival (Goldberg et al. 2010 and Malcovati et al. 2007). Best supportive care for all patients includes clinical monitoring, red blood cell (RBC) and platelet transfusions for symptomatic anemia or thrombocytopenia, psychosocial support, and quality-of-life assessments. Daily iron chelation with subcutaneous deferoxamine or oral deferasirox should be considered to decrease iron overload in patients receiving >20 to 30 RBC transfusions. In addition, hematopoietic growth factor support, such as erythropoietin, granulocyte colony-stimulating factor, or granulocyte/macrophage colony-stimulating factor, should be considered for symptomatic cytopenias that are unresponsive to correction of all other identifiable causes of the low blood counts.

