4.3 CONCOMITANT THERAPY

4.3.1 Permitted Therapy

Concomitant therapy includes any medication (e.g., prescription drugs, over-the-counter drugs, herbal/homeopathic remedies, nutritional supplements) used by a patient from 4 weeks prior to screening to the end-of-study visit/early termination visit.

Throughout the study, patient could be treated with any concomitant medications or treatment necessary to provide adequate supportive care except for those treatments listed in the prohibited therapy. Upon physician discretion and their normal practice, G-CSF can be used.

All RBC transfusions administered during the study should be documented (i.e., specified by number of units transfused) and recorded on the eCRF.

All concomitant medications should be reported to the investigator and recorded on the Concomitant Medications electronic Case Report Form (eCRF).

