4.3.2 Prohibited Therapy

The following treatments are prohibited during study treatment:

Investigational or unlicensed/unapproved agents of any type

Patients receiving any of the prohibited therapies will be discontinued and assessed for safety at end-of study visit

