6.4.2 Secondary Efficacy Endpoints

Secondary efficacy endpoints include platelet and neutrophil response at week 12, defined by the following IWG 2006 criteria and will analyzed for the PP population.

- % patients with platelet response (pre-treatment $< 100 \times 10^9/L$) at week 12 defined by IWG 2006 as following:
 - Absolute increase of $\geq 30 \times 10^9/L$ for patients starting with $> 20 \times 10^9/L$ platelets (Increase from $< 20 \times 10^9/L$ to $> 20 \times 10^9/L$ and by at least 100%)
- % patients with neutrophil response (pre-treatment $< 1.0 \times 10^9/L$) at week 12 defined by IWG 2006 as following:
 - At least 100% increase and an absolute increase $> 0.5 \times 10^9/L$

The percentages of patient who achieve the above hematologic responses at week 12, according to the IWG 2006 criteria will be presented in summary tables.

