Marrow Blasts	< 5%	5% - 10%	-	11% - 20%	21% - 30%
Karyotype	Good: Normal isolated -Y, isolated del(5q) or isolated del(20q)	Intermediate: All karyotypes not defined as Good or Poor	Poor: Abnormal chromosome 7 or A complex karyotype (3 or more anomalies)	-	-
Peripheral blood cytopenias ^b	0 or 1	2 or 3	-	-	-

^a sum all 3 for overall IPSS score

^b IPSS definition of Peripheral Blood Cytopenias: Haemoglobin < 10 g/dL, Absolute neutrophil count < 1,500/mm³, Platelet count < 100,000/mm³

Appendix 3
International Working Group (IWG) Response Criteria for MDS
 (Cheson et al. Blood. 2006;108:419 - 425)

IWG Criteria for Response		
Category	Original (sustained \geq weeks)	Modified (sustained \geq 4 weeks)
CR: Marrow	< 5% blasts; no dysplasia; normal maturation of all cell lines	\leq 5% blasts; normal maturation of all cell lines
CR: Peripheral blood	Hgb \geq 11 g/dL; ANC \geq 1,500/mL; platelets \geq 100,000/mL; 0% blasts; no dysplasia	Hgb \geq 11 g/dL; ANC \geq 1000/mL; platelets \geq 100,000/mL; 0% blasts; hematologic improvement responses noted in addition to marrow CR
PR	Same as CR, except blasts \downarrow by \geq 50% or lower FAB	Same as CR, except blasts \downarrow by \geq 50%, still greater than 5% in marrow
IWG Criteria for Hematological Improvement		
Category	Pretreatment	Modified IWG Response Criteria* (\geq 8 weeks)
Erythroid (HI-E)	Hgb < 11 g/dL	Hgb \uparrow of \geq 1.5 g/dL
		\downarrow of \geq 4 RBC transfusions/8 weeks versus pretreatment requirement in previous 8 weeks; only RBC transfusions given for a pretreatment Hgb of \leq 9.0 g/dL count
Platelet (HI-P)	< 100,000/mL	\uparrow of \geq 30,000/mL (starting with $>$ 20,000/mL)
		\uparrow from $<$ 20,000/mL to $>$ 20,000/mL by \geq 100%
Neutrophil (HI-N)	< 1,000/mL	\uparrow of \geq 100% and $>$ 500/ μ L
Progression/Relapse after hematological improvement		\geq 1 of the following: \geq 50% decrement from maximum response levels in granulocytes or platelets; \downarrow in Hgb by \geq 1.5 g/dL; transfusion dependence

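### Platelet response at week 12 carries no condition on platelet transfusion, and such transfusions are not named in the trial's transfusion record, so a transfusion-raised count can be scored as a response

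*Protocol*

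**What the plan says.** **Endpoint.** Protocol section 3.4.1 lists as a secondary outcome the percentage of "patients with platelet response (pre-treatment $< 100 \times 10^9/L$) at week 12 defined by IWG 2006 as following". There are two routes to response. One is "Absolute increase of $\geq 30 \times 10^9/L$ for patients starting with $> 20 \times 10^9/L$ platelets". The other, for a start below 20 x 10^9/L, is a count that passes 20 and at least doubles. Section 6.4.2 repeats these criteria and adds: "The percentages of patient who achieve the above hematologic responses at week 12, according to the IWG 2006 criteria will be presented in summary tables". Neither section mentions platelet transfusion.

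**Permitted care.** Section 1.1 includes "red blood cell (RBC) and platelet transfusions for symptomatic anemia or thrombocytopenia" in best supportive care for this disease. Section 4.3.1 says "patient could be treated with any concomitant medications or treatment necessary to provide adequate supportive care except for those treatments listed in the prohibited therapy". The only entry under prohibited therapy in section 4.3.2 is "Investigational or unlicensed/unapproved agents of any type". Platelet transfusion is therefore allowed.

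**Records.** Section 4.3.1 states: "All RBC transfusions administered during the study should be documented (i.e., specified by number of units transfused) and recorded on the eCRF". Sections 4.4.2.1 to 4.4.2.3 and a row in Appendix 1 also require a transfusion record, again for red cells only. Separately, those sections and another Appendix 1 row require concomitant treatment to be recorded at every visit from screening to end of study.

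**Response criteria.** Appendix 3 reproduces the IWG criteria. The column that holds the erythroid, platelet and neutrophil improvement rules is headed "Modified IWG Response Criteria* (\geq 8 weeks)".

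**The concern.** A platelet transfusion raises the quantity that the endpoint measures. Its use points to a low or falling count, yet a count taken soon afterwards can satisfy the response rule. The second route is written for patients starting below 20 x 10^9/L, and eligibility sets no platelet floor, so the plan foresees the patients in whom transfusion is most plausible.

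The study has one arm, so no control group shares the error and any false response goes directly into the reported percentage. At baseline the error runs the other way. A transfused pre-treatment count raises the level from which the rise is measured, or lifts the patient to 100 x 10^9/L or above and so out of the denominator.

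The primary endpoint shows that the authors considered transfusion for red cells: it has a transfusion-reduction criterion and a rule on which transfusions count. The platelet endpoint has no counterpart. An analysis rule added later works only if the date of each platelet transfusion was collected.

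**Working it through.** **1. Does the definition admit a transfusion-raised count?** The rule in 3.4.1 and 6.4.2 uses only the pre-treatment count and the week-12 count.
- Start above 20: any rise of 30 x 10^9/L or more passes, whatever its cause.
- Start at x below 20: a rise of 20 gives x + 20, which exceeds 20, and the relative rise 20/x exceeds 100%. It passes for every such x.

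Suppose a transfusion lifts the count at sampling by 20 to 60 x 10^9/L (an assumption; the protocol gives no figure). Every patient starting below 20 would then qualify. Of those starting above 20, only patients with a lift of 30 or more would.

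**2. Would the record reveal it?**

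| Item | Red cells | Platelets |
|---|---|---|
| Named in 4.3.1 | yes, by units | no |
| Named in 4.4.2.1 to 4.4.2.3 | yes | no |
| Own row in Appendix 1 | yes | no |
| General concomitant-treatment record | separate item | possible, not named |

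The general record is required at every visit. However, 4.3.1 describes concomitant therapy as medication, with drugs, herbal remedies and supplements as examples, and then treats transfusion separately, for red cells only. Sites could differ on whether a platelet transfusion belongs there, and no date is expressly required.

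**3. Does Appendix 3 close the gap?** Counts are scheduled at weeks 0, 4, 8 and 12. If a rise must last at least 8 weeks up to week 12, it must be present from week 4 on. A single transfusion shortly before week 12 would then not qualify. Repeated transfusions, or a transfused baseline count, would still distort the result. Sections 3.4.1 and 6.4.2 cite the IWG criteria but write out their own thresholds at week 12 without the duration, so which text governs is open.

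**4. Size.** The protocol states no figure for platelet response. Its evaluable number reproduces: 120 x (1 - 0.10) = 108. The share of patients starting below 100 x 10^9/L is not given; assume 10% to 40%.
- 0.10 x 108 = 10.8, about 11 patients; one false responder adds 1/11 = 9.1 percentage points.
- 0.40 x 108 = 43.2, about 43 patients; one false responder adds 1/43 = 2.3 percentage points.

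The number of false responders cannot be obtained from the documents and may be zero.

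**The case against.** The strongest reply has four parts.

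**The record exists.** A reader might infer that platelet transfusions go unrecorded. The protocol does not support that: if a transfusion is permitted as concomitant treatment, it can be recorded as concomitant treatment, and that record is required at every visit. This stands. What remains is narrower: the transfusion is not named and its date is not expressly required.

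**The criteria include a duration.** A reader might infer that any transfused patient is scored as a responder. That is too strong. It takes a baseline below 100 x 10^9/L, a transfusion close enough to the week-12 count to cross the threshold, and a reading in which the 8-week heading does not apply. The claim that survives is that such a count can be scored as a response. The unresolved conflict between body and appendix is part of the problem.

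**The SAP can handle it.** Rules on evaluable laboratory values often belong in the SAP, which is not shown and may contain one. That is fair for the analysis rule. It does not cover data capture: an SAP cannot apply a window to dates that sites were not clearly asked for.

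**The size is assumed.** One could combine 5 false responders with 30 patients to reach 5/30 = 17 points. Neither number is in the protocol, the pairing is the most unfavourable one, and it supposes that none of the five would have responded anyway. The protocol gives no platelet transfusion rate, and its patients are lower-risk and must have been stable for a month before entry. This objection stands, and no total inflation is claimed here.

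**Conclusion.** The point holds as a modest defect in endpoint definition and data capture. As written, a week-12 count raised by a recent platelet transfusion can meet the response rule, and a raised baseline count can mask a response, unless the 8-week criterion in Appendix 3 governs. The error at week 12 can only raise the reported percentage; the error at baseline mainly lowers it.

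Per false responder the effect is about 2 to 9 percentage points, on the assumption that 11 to 43 of 108 patients start below 100 x 10^9/L. It is zero if nobody is transfused near a relevant count. Platelet response is a descriptive secondary endpoint without a stated test. The primary endpoint, the sample size and the stated precision are not touched.

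**What to change.** 1. In section 4.3.1 and the Appendix 1 transfusion row, name platelet transfusions alongside red-cell transfusions and require their dates. Align sections 4.4.2.1 to 4.4.2.3.
2. In sections 3.4.1 and 6.4.2, count a baseline or week-12 platelet value only if no platelet transfusion was given in a prespecified period before it (7 days, for example; the length is for the trial team to justify). Score a patient with no qualifying week-12 value as a non-responder. Because Appendix 1 takes a blood count at both screening and week 0, also say which one is the pre-treatment value.
3. State whether the 8-week criterion in Appendix 3 applies to platelet response, and make the week-12 wording agree with it.

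The cost is one extra eCRF field, a few words in the endpoint definition, and possibly a slightly lower reported platelet response rate. Patient care does not change.

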3.4.2 Safety Outcome Measures

The safety outcome measures for this study are as follows:

Tolerability and safety of Recormon® (Incidence, nature, and severity of adverse events)

Safety assessments will include AEs, SAEs, routine safety laboratory tests, vital signs measurements, and recording of concomitant medications. All clinical AEs and SAEs as well as laboratory abnormalities will be recorded and graded according to the NCI-CTCAE version 4.0.

Patients will undergo an end-of-study safety assessment 4 weeks after the last Recormon® administration or after early withdrawal (unless the reason for early withdrawal is withdrawal of consent)

4. MATERIALS AND METHODS

4.1 PATIENTS

Adult anemic MDS patients (≥ 18 years old) in the low or intermediate 1 risk group according to the International Prognostic Scoring System (IPSS)

4.1.1 Inclusion Criteria

Patients must meet the following criteria for study entry:

- Able and willing to provide written informed consent and to comply with the study protocol
- Adult patients (≥ 18 years old)
- Low or intermediate-1 risk MDS (having IPSS risk score ≤ 1) confirmed with bone marrow morphology analysis and karyotyping within 6 months prior to screening
- No previous treatment with hematopoietic growth factors within 3 months prior to screening
- Symptomatic anemia ($Hb < 10 \text{ g/dL}$) as determined by investigator
- Serum Erythropoietin $< 500 \text{ mU/ml}$ within 14 days prior to the first dose of study treatment
- Require no red blood cell transfusion or dependent on < 4 units within 8 weeks prior to screening
- Clinically stable for at least one month prior to entry into the study as determined by investigator
- For female patients of childbearing potential and male patients with partners of childbearing potential, agree (by patient and/or partner) to use highly effective form(s)

Recormon—F. Hoffmann-La Roche Ltd

Protocol ML29005, Version 3.0 dated 12 Sep 2016

25

of contraception (i.e., one that results in a low failure rate [$< 1\%$ per year] when used consistently and correctly)

4.1.2 Exclusion Criteria

- Patients who meet any of the following criteria will be excluded from study entry:
- Contraindications and/or known hypersensitivity to the active substance and/or any of the excipients of Recormon® treatment according to the approved package insert
- Poorly controlled hypertension as assessed by the investigator
- History of Acute myeloid leukemia (AML) or high risk for AML
- Previously documented evidence of Pure red cell aplasia (PRCA)
- Current pregnancy or breast-feeding
- High likelihood of early withdrawal or interruption of the study
- Administration of another investigational drug within 1 month before screening or planned during the study period

4.2 STUDY TREATMENT

4.2.1 Formulation, Packaging, and Handling

4.2.1.1 Recormon®

Recormon® will be supplied by the sponsor as solution for injection in pre-filled syringes.

For further details, see the local prescribing information.

4.2.2 Dosage, Administration and Compliance

4.2.2.1 Dosage and administration of Recormon®

Injectable solution of Recormon® 30,000 or 60,000 IU per week administered subcutaneously

The initial dose is 30,000 IU per week administered subcutaneously

Response will be firstly evaluated at week 4 (visit 2):

- If haemoglobin level reaches ≥ 12 g/dL at any time, Recormon® should be discontinued until Hb levels are ≤ 10 g/dL
- If the haemoglobin level increases < 1 g/dL from screening level and haemoglobin level < 12 g/dL, a 60,000 IU weekly of Recormon® will be administered subcutaneously until week 12.
- If the haemoglobin level increases ≥ 1 g/dL from screening level and haemoglobin level < 12 g/dL, a 30,000 IU weekly of Recormon® will be continued until week 12

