The study consists of a 2-week screening period, a 12-week treatment phase and end-of-study visit (see figure 1). After screening, eligible patients will be treated with epoetin beta (Recormon®) as recommended in the approved label and international guidelines for the use of epoetin in MDS patients, Recormon® dosage will be adjusted on the basis of erythroid response.

During screening period, serum level of endogenous erythropoietin will be assessed, as well as liver and kidney function. Bone marrow morphology analysis and karyotyping are also performed during screening if they have not been assessed in the 6 months prior to participation in the study. Complete blood count test is performed during screening period and at every patient's visit until the end of study visit. The result should be available on visit date, prior to the Recormon® administration

The patient's erythroid response will be assessed at week 4 and every 4 weeks thereafter, until end-of-study visit. Patients who achieve Hb level ≥ 12 g/dL will stop treatment, while patients with Hb level <12 g/dL will continue treatment for the total of 12 weeks. Concurrent G-CSF can be administered upon physician discretion.

Number of Patients

120 patients expected to be enrolled.

Target Population

Adult anemic MDS patients (≥ 18 years old) in the low or intermediate-1 risk group according to the International Prognostic Scoring System (IPSS)

Inclusion Criteria

Patients must meet the following criteria for study entry:

1. Able and willing to provide written informed consent and to comply with the study protocol
2. Adult patients (≥ 18 years old)
3. Low or intermediate-1 risk MDS (having IPSS risk score ≤ 1) confirmed with bone marrow morphology analysis and karyotyping within 6 months prior to screening
4. No previous treatment with hematopoietic growth factors within 3 months prior to screening
5. Symptomatic anemia ($Hb < 10$ g/dL) as determined by investigator
6. Serum Erythropoietin < 500 mU/ml within 14 days prior to the first dose of study treatment.
7. Require no red blood cell transfusion or dependent on < 4 units within 8 weeks prior to screening
8. Clinically stable for at least one month prior to entry into the study as determined by investigator

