- Absolute increase of $\geq 30 \times 10^9/L$ for patients starting with $> 20 \times 10^9/L$ platelets (Increase from $< 20 \times 10^9/L$ to $> 20 \times 10^9/L$ and by at least 100%)
- % patients with neutrophil response (pre-treatment $< 1.0 \times 10^9/L$) at week 12 defined by IWG 2006 as following;
- At least 100% increase and an absolute increase $> 0.5 \times 10^9/L$

Safety Outcome Measures

The safety outcome measures for this study are as follows:

- Tolerability and safety of Recormon®

Investigational Medicinal Products

Injectable solution of Recormon® (provided free of charge by Roche) 30,000 or 60,000 IU per week administered subcutaneously

The initial dose is 30,000 IU per week administered subcutaneously

- Response will be firstly evaluated at week 4 (visit 2):
 - If haemoglobin level ≥ 12 g/dL at any time, Recormon® should be discontinued until Hb levels are ≤ 10 g/dL
 - If the haemoglobin level increases < 1 g/dL from screening level and haemoglobin level < 12 g/dL, a 60,000 IU weekly of Recormon® will be administered subcutaneously until week 12
 - If the haemoglobin level increases ≥ 1 g/dL from screening level and haemoglobin level < 12 g/dL, a 30,000 IU weekly of Recormon® will be continued until week 12

Non-Investigational Medicinal Products

Upon physician discretion, G-CSF can be used concurrently

Statistical Methods

Descriptive statistics will be used for baseline characteristics. The interim data analysis will be performed when the first 30 patients completing 12-week treatment period.

Determination of sample size

Sample size based on a 5% significance level and the 80% power with 10% drop out resulting of 120 patients in total.

Safety: Assuming a 10% withdrawal rate, 120 patients will be enrolled such that we expect 108 patients will not withdraw and will remain evaluable. With 108 evaluable patients in this study, the sample size is sufficient to have at least 95% probability of observing a particular adverse event in at least one patient in this study, if the true proportion of patients in the target population as a whole who experience this event is 0.0274 i.e. approximately 1 in every 37 patients.

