3. STUDY DESIGN

3.1 DESCRIPTION OF STUDY

3.1.1 Overview of Study Design

This is a phase IV, prospective, multi-centre, open label study to assess the efficacy of Recormon® for treating anemic patients with low/intermediate-1 risk MDS, in approximately 120 adult patients. The primary efficacy endpoint is a proportion of patients achieving erythroid response at week 12 according to IWG 2006 definition. The trial will be conducted at approximately 8 centres nationwide.

All potential study patients must provide signed written informed consent approved by the relevant independent Ethics Committee before undergoing any study-specific procedures. Results of the screening assessments must be available and patients must meet all eligibility criteria prior to enrolment into the study. The study design is shown in Figure 1.

[figure not shown]

Figure 1 Study Scheme

The study consists of a 2-week screening period, a 12-week treatment phase and end-of-study visit (see figure 1). After screening, eligible patients will be treated with epoetin beta (Recormon®) as recommended in the approved label and international guidelines for the use of epoetin in MDS patients, Recormon® dosage will be adjusted on the basis of erythroid response.

During screening period, serum level of endogenous erythropoietin will be assessed, as well as liver and kidney function. Bone marrow morphology analysis and karyotyping are also performed during screening if they have not been assessed in the 6 months prior to participation in the study. Complete blood count test is performed during screening period and at every patient's visit until the end of study visit. The result should be available prior to dosing of Recormon®.

The patient's erythroid response will be assessed at week 4 and every 4 weeks thereafter, until end-of-study visit. Patients who achieve Hb level ≥ 12 g/dL will stop treatment, while

Recormon—F. Hoffmann-La Roche Ltd

Protocol ML29005, Version 3.0 dated 12 Sep 2016

23

patients with Hb level < 12 g/dL will continue treatment for the total of 12 weeks. Concurrent G-CSF can be administered upon physician discretion.

Patients can withdraw from the study at any time as per section 4.5.1

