4.4.2.2 Assessments during Treatment

All assessments must be performed on the day of the specified visit (V1 – V4), unless a time window is specified in the schedule of assessments (see Appendix 1). Assessments scheduled on the visit date should be performed prior to administration of study treatment, unless otherwise noted in the schedule of assessments.

At each treatment visit, patients will undergo the following assessments:

- Physical examination and measurements of vital signs
- Routine laboratory tests (see section 4.4.1.4 for details about individual laboratory assays). The results from these tests should be available on visit date prior to the Recormon® administration.
- AE recording
- Recording concomitant treatments and therapies
- Recording RBC transfusion needed from previous visit
- Recormon® dose adjustment will be performed at week 4±1 (see section 4.2.2.1 for details about dose adjustment)

Please see Appendix 1 for the schedule of assessments performed during the treatment period.

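### At Hb ≥ 12 g/dL the protocol says both that treatment stops and that it is only held until Hb ≤ 10 g/dL; on one reading a patient stopped at V2 could lack the week-12 data for the primary endpoint

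*Protocol*

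**What the plan says.** Two rules for the same event stand in the current protocol text.

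- **Stop.** The synopsis study description reads "Patients who achieve Hb level ≥ 12 g/dL will stop treatment, while patients with Hb level <12 g/dL will continue treatment", and 3.1.1 has the same contrast. Those below 12 g/dL complete 12 weeks; those at or above it stop. Neither place mentions a restart.
- **Hold.** 4.2.2.1 reads "If haemoglobin level reaches ≥ 12 g/dL at any time, Recormon® should be discontinued until Hb levels are ≤ 10 g/dL". The dosing part of the synopsis says "If haemoglobin level ≥ 12 g/dL at any time, Recormon® should be discontinued until Hb levels are ≤ 10 g/dL", and Appendix 1 footnote f repeats the rule. The synopsis therefore carries both versions.

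Three further provisions decide what follows for data collection.

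- Section 3.2: "The end-of-study visit will occur 4 weeks after" the patient's last dose. 4.4.2.3 and Appendix 1 footnote a use the same interval, and 4.5.1.1 sends patients who come off drug early to that visit.
- Section 3.1.1: "erythroid response will be assessed at week 4 and every 4 weeks thereafter, until end-of-study visit".
- The primary outcome in 3.4.1 is "The cumulative proportion of patients achieving erythroid response at week 12 according to IWG 2006 definition".

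**The concern.** A site that follows 3.1.1 ends treatment at Hb ≥ 12 g/dL; a site that follows 4.2.2.1 interrupts it and waits. Dosing can therefore differ between sites. The larger point is follow-up. Because the end-of-study visit is tied to the last dose and response is assessed only up to that visit, ending treatment at V2 can bring the final visit forward to well before week 12.

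The patients exposed to this are likely responders. Entry requires Hb below 10 g/dL, so reaching 12 is a rise of more than 2 g/dL against a response threshold of 1.5. If their week-12 haemoglobin and transfusion counts are not collected, an analysis plan can say how to score the gap but cannot recover the values.

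**Working it through.** **Inputs.** Weekly dosing (4.2.2.1). Blood results read before the visit-day dose (4.4.2.2). Visits at weeks 0, 4, 8 and 12 (V1 to V4) and end of study at week 15, with ±1 week on V2, V3, V4 and the end-of-study visit (Appendix 1). End-of-study visit = last dose + 4 weeks (3.2, 4.4.2.3, footnote a). Entry Hb < 10 g/dL (4.1.1). Response threshold ≥ 1.5 g/dL (3.4.1). 120 enrolled, 108 evaluable, 95% half width 0.0817 at a rate of 0.25 (6.1).

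**1. Reproduce the protocol's own figures.** Weekly doses at weeks 0 to 11 put the last dose of a full course at week 11, and 11 + 4 = 15, the week in Appendix 1. So the dating convention used below is the protocol's. The half width also reproduces: 1.96 × √(0.25 × 0.75 / 108) = 0.0817.

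**2. Stop at V2, held in week w.** The visit-day dose is not given, so the last dose is at w − 1 and the end-of-study visit at (w − 1) + 4 = w + 3.
- w = 4: week 7.
- w = 3 to 5 (V2 window): weeks 6 to 8.
- Adding the end-of-study window of ±1: weeks 5 to 9.

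V4's window is 12 ± 1 = weeks 11 to 13. The smallest gap is 11 − 9 = 2 weeks, so this visit cannot stand in for V4.

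**3. Hold at V2 with no restart.** The last dose is again at week 3, so applying the last-dose rule literally gives week 7 here too. Week 7 comes before V3 at week 8, the next scheduled blood count at which a fall to 10 g/dL could be seen.

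**4. Stop at V3.** Last dose at week 7; 7 + 4 = week 11, inside V4's window. If V3 falls in weeks 7 to 9, the nominal date is week 10 to 12; the week-10 case reaches V4's window only through the end-of-study visit's own +1 week. Blood count and transfusion record are both scheduled at that visit, so a V3 stop is not counted as a loss.

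**5. Length of observation after V2.** For a V2 stop, nominally 7 − 4 = 3 weeks, at most 4. From V2 to V4 it is 12 − 4 = 8 weeks.

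**6. Doses at stake on scheduled visits.** Held at V2 and restarted at V3: weeks 8, 9, 10 and 11, so at most 4 doses separate the two rules. Held at V3: 0, because nothing is dispensed at V4.

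**7. Who is affected.** Taking entry Hb as baseline, the rise at Hb ≥ 12 g/dL exceeds 12 − 10 = 2 g/dL, above 1.5.

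**8. Scale.** One patient scored differently moves the rate by 1/120 = 0.83 points (1/108 = 0.93 on the evaluable number), against a planned half width of 8.17 points. The number of such patients cannot be derived from the protocol.

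**The case against.** The case for reading the text as a hold with visits kept is good.

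- The operative dosing rule is stated the same way in three places. 4.4.2.2 says "dose adjustment will be performed at week 4±1" and refers to 4.2.2.1 for the details. The stop wording is overview text and does not say permanently.
- A hold that ends when Hb falls to 10 g/dL works only if Hb is still measured, and the scheduled places for that are V3 and V4. While the hold is open, nobody knows that the week-3 dose was the last.
- Footnote f is attached to drug dispensing. The blood-count and transfusion rows carry no Hb condition, and 4.4.2.2 requires assessments at V1 to V4. Hb ≥ 12 g/dL is not among the discontinuation reasons in 4.5.1.1, although that list is not exhaustive.
- Few patients may be involved. 3.3.1 says improvement is usually seen at 6 to 8 weeks, so a rise above 2 g/dL by week 4 may be uncommon.
- The word cumulative in 3.4.1 may credit a rise seen before week 12. Even a patient who left at week 7 would have blood counts at V2 and at the final visit.

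All of this stands as a limit on the claim. A reader might infer that the protocol sends V2 stops home at week 7; it does not say so, and no passage cancels V3 or V4. A reader might also infer that the response rate is biased downward. That would need response to be judged on the missing week-12 value, or on the 8-week duration heading in Appendix 3, and the protocol settles neither. The duration question is also separate: a patient first responding at V3 has only 4 weeks by week 12 under either rule.

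What the objection does not remove is that 3.1.1, read with 3.2 and 4.5.1.1 as written, permits the early exit, and no sentence tells a site to keep V3 and V4.

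**Conclusion.** The inconsistency is real and should be corrected. The synopsis study description and 3.1.1 stop treatment at Hb ≥ 12 g/dL; the synopsis dosing text, 4.2.2.1 and Appendix 1 footnote f hold it. The hold is probably what is intended.

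On the stop reading, or with the last-dose rule applied to a hold that is never restarted, a V2 stop has its end-of-study visit at about week 7 (week 5 to 9 with windows), at least 2 weeks before V4's window opens. Such a patient could lack the week-12 haemoglobin and transfusion record. This assumes weekly doses on schedule and the visit-day dose withheld. V3 stops are nominally unaffected.

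The effect on the response rate is likely small and cannot be estimated. It depends on how many patients reach 12 g/dL by V2, which the protocol does not give, and on whether an earlier rise counts. If it does, little or nothing is lost. Any loss would fall on likely responders, so its direction would be downward, but a bias is possible rather than shown.

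**What to change.** 1. In the synopsis study description and in 3.1.1, replace the statement that treatment stops with one that Recormon is held until Hb is 10 g/dL or below, matching 4.2.2.1.
2. Add one sentence, in 4.4.2.3 or Appendix 1 footnote a: patients whose drug is held or stopped for Hb ≥ 12 g/dL still attend V3 and V4 with blood count and transfusion record; their end of study is no earlier than V4; the 28-day post-dose safety assessment is unchanged.

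The cost is amendment wording and a small visit burden. For a V2 stop, the week-7 safety assessment falls in V3's window (weeks 7 to 9), so V4 is nominally the one added attendance. For a V3 stop, the week-11 assessment falls in V4's window and nothing is added. The adverse-event period in 5.3.1 and the sample size stay as they are, and no new tests are needed.
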